Effects of agonists of glucagon like peptide - 1 receptors (GLP-1R) on arterial stiffness, endothelial glycocalyx and coronary flow reserve in patients with coronary artery disease and patients with diabetes mellitus

ClinicalTrials.gov Identifier: NCT03010683

Document date: December 22, 2016

Study Protocol

Objectives

Arterial stiffness is associated with increased risk for cardiovascular disease. Moreover, the integrity of endothelial glycocalyx plays a vital role in vascular permeability, inflammation and elasticity. Agonists of glucagon like peptide - 1 receptors (GLP-1R) used in the treatment of type 2 diabetes mellitus (T2DM). This category includes exenatide and liraglutide. These drugs lower glucose levels by inhibiting the secretion of glucagon, promoting the release of insulin in response to hyperglycemia, slowing gastric emptying, and augmenting satiety. Clinical studies have shown that GLP-1R agonists have beneficial effects on cardiovascular function in both diabetic patients and healthy subjects. The purpose of this study is to investigate in patients with T2DM without coronary artery disease (CAD), patients with T2DM and CAD and obese patients with abnormal oral glucose tolerance test (OGTT), changes in arterial stiffness,

endothelial glycocalyx thickness and coronary reserve flow (CFR) after treatment with metformin or agonist GLP-1R.

Design

The investigators will study three groups matched for age and sex: 30 patients with type 2 diabetes mellitus (T2DM) without coronary artery disease (CAD), 30 patients with T2DM and CAD and 30 obese patients (BMI >30 Kg/m²) with abnormal oral glucose tolerance test (OGTT). It will be a randomized study with metformin or GLP-1R agonist treatment for 1 year. All subjects will receive for 1 year: (a) GLP-1R agonist or (b) metformin. At 0, 3, 6 and 12 months, where 0 is the starting point of treatment, blood samples will be collected.

Methods

At 0, 3, 6 and 12 months the investigators will measure:

- a. Carotid-femoral pulse wave velocity (PWV, m/sec) using tonometry by Complior (SP ALAM) and augmentation index (AI, %) by the method of arteriography (Arteriograph, TensioMed)
- b. Perfused boundary region (PBR, micrometers) of the sublingual arterial microvessels (ranged from 5-25 micrometers) using Sideview Darkfield imaging (Microscan, Glycocheck). Increased PBR is considered an accurate noninvasive index of reduced endothelial glucocalyx thickness.
- c. Coronary flow reserve (CFR) in the left anterior descending artery after infusion of adenosine using Doppler echocardiography.
- d. Determination of the following parameters in blood: glucose, insulin, free fatty acids, triglycerides, glycerol, C reactive protein (CRP), transforming

growth factor-b (TGF-b), Lipoprotein-Associated Phospholipase A2 (LP-LPA2), tumor necrosis factor-a (TNF-a), interleukins 6 and 10 (IL6 and IL10), propeptide of type I procollagen (PIP), propeptide of procollagen type III (PIIINP), matrix metalloproteinases 9 and 2 (MMP), macrophage-colony stimulating factor (M-CSF), growth differentiation factor-15 (GDF-15), N-terminal pro b-type natriuretic peptide (NT-proBNP) and galectin-3.

Statistical analysis

All comparisons will be performed with the Statistical Package for Social Sciences 21.0 for Windows (SPSS Inc., Chicago, Illinois, USA). Categorical data will be compared between patients by contingency tables. Continuous variables will be tested for normality using the Kolmogorov-Smirnov test. Normally distributed variables will be given as mean \pm standard deviation. Data with a non-gaussian distribution will be expressed as median (interquartile range) and will be analyzed after transformation into ranks. Differences in mean values for each of the measured variables will be compared by t-test or paired t-test for continuous variables. For non-normally distributed data Mann Whitney or Wilcoxon signed-rank test will be used. The investigators will use parametric (Pearson r) and non-parametric (Spearman ρ) correlation coefficients to examine cross-sectional associations. ANOVA (general linear model, SPSS 22, SPSS Inc, Chicago, Ill) for repeated measurements will be applied a) for measurements of the examined markers at baseline, 3, 6 and 12 months after treatment used as a within-subject factor b) for the effects of treatment (liraglutide vs metformin), as a between-subject factors. The F and P

values of the interaction between time of measurement of the examined markers and type of treatment will be calculated. The F and P values of the comparison between treatments will be calculated. The Greenhouse-Geisser correction will be used when the sphericity assumption, as assessed by Mauchly's test, will not be met. Post hoc comparisons will be performed with Bonferroni correction.

Comparisons between baseline or post-treatment values of measured markers between the 2 treatment groups will be performed using factorial ANOVA. Post hoc comparisons will be performed with Bonferroni correction. Statistical significance will be considered as $p < 0.05$. Baseline variables that will be statistically different ($p < 0.05$) among the 2 study groups or will be of clinical significance (HbA1c, weight, BMI and waist circumference) will be included in multivariate models as covariates.

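### The protocol does not say that drug is randomised within each of the three populations, and its only stated balancing device, age and sex matching, does not balance the drug arms

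*Combined protocol and SAP*

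**What the plan says.** The Objectives section frames the question by population: "The purpose of this study is to investigate in patients with T2DM without coronary artery disease (CAD), patients with T2DM and CAD and obese patients". The last of these groups is defined by its glucose tolerance result. The Design section sets 30 patients for each and describes one balancing device: "The investigators will study three groups matched for age and sex". These groups are the disease populations, not the drug arms.

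On allocation, the Design section says "It will be a randomized study with metformin or GLP-1R agonist treatment for 1 year" and then "All subjects will receive for 1 year: (a) GLP-1R agonist or (b) metformin". No section gives a ratio, a method of generating or concealing the sequence, blocks, strata, or the level (overall or within population) at which patients are randomised.

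In the Statistical analysis section, the repeated-measures ANOVA has time as the within-subject factor and is used "for the effects of treatment (liraglutide vs metformin), as a between-subject factors". A second analysis reads: "Comparisons between baseline or post-treatment values of measured markers between the 2 treatment groups will be performed using factorial ANOVA". Its factors are not listed. The covariates are HbA1c, weight, BMI and waist circumference, plus any baseline variable that differs between the two study groups at p<0.05. Population is not named as factor, stratum or covariate.

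**The concern.** The named treatment tests set drug against drug, so the balance that matters is between the drug arms, overall and inside each population. Age and sex matching across populations does nothing for that. Only the randomisation can, and nothing written ties it to population.

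Two things are at stake. First, the purpose names three groups of 30. If one of them splits unevenly by drug, the drug contrast in that group loses precision. Second, the populations are defined by diabetes and CAD, so they can be expected to differ on coronary flow reserve, arterial stiffness and glycocalyx measures. If one arm holds more CAD patients, and CAD patients also change differently over the year, part of that difference enters the pooled time-by-treatment result. As written, the model has no population term to remove it.

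**Working it through.** The plan states no allocation ratio, imbalance probability or power, so there is no figure to reproduce. The check asks what could happen if allocation ignored population.

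**Inputs.** From the Design section: three populations of 30, so 3 × 30 = 90 patients, and two drugs. Assumed: 1:1 allocation, no dropout and, for power, two-sided alpha 0.05.

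**1. Chance of an uneven split.** For simple randomisation, the number on one drug in a population is binomial(30, 0.5). The probability for any of three populations is 1 − (1 − p)³. For an overall 45:45 list the number is hypergeometric (30 drawn from 90, 45 on each drug). The any-of-three figure comes from the joint distribution.

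| Split or worse | Simple, one population | Simple, any of three | 45:45 list, one population | 45:45 list, any of three |
|---|---|---|---|---|
| 19:11 | 20.0% | 48.9% | 11.7% | 26% |
| 20:10 | 9.9% | 26.8% | 4.3% | 10.7% |

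For example, 1 − (1 − 0.0987)³ = 0.268. With completed blocks inside each population, each splits 15:15.

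**2. Cost in precision within a population.** The variance of the drug contrast is proportional to 1/a + 1/b.
- 15:15 gives 2/15 = 0.133, and 20:10 gives 1/20 + 1/10 = 0.150. The ratio is 0.150/0.1333 = 1.125, so the standard error rises by √1.125 − 1 = 6%.
- 19:11 gives a ratio of 1.077.
- Averaged over the binomial distribution of splits, the ratio is 1.037, a rise of about 4%.
- Two-sample t-test power (noncentral t) falls from 56% at 15:15 to 51% at 20:10 for an assumed difference of 0.8 SD, and from 75% to 70% for 1.0 SD.

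**3. Composition of the arms in the pooled comparison.** Under 45:45, the number of CAD patients on one drug has variance 30 × (1/2)(1/2) × 60/89 = 5.06, or SD 2.25. The difference in CAD share between arms is (2x − 30)/45, with SD 2 × 2.25/45 = 0.10.
- Level: if CAD patients sit 0.8 SD lower on coronary flow reserve (assumed), the arm difference due to composition has SD 0.8 × 0.10 = 0.08, and it exceeds 0.1 SD in 26% of allocations. For an assumed gap of 0.5 SD the figures are 0.05 and 4%.
- Change: a 19:11 split gives a share difference of 8/45 = 0.178. If CAD patients' change over the year differed from the others' by an assumed 0.5 to 0.8 SD, the drug contrast in change would shift by 0.178 × 0.5 = 0.09 to 0.178 × 0.8 = 0.14 SD. If their change does not differ, the shift is zero.

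**4. Would the covariate rule catch it?** Take 45 per arm and treat CAD status as a baseline variable.
- 20 v 10: chi-square 5.0, p = 0.025 (Fisher 0.043). The rule is triggered.
- 19 v 11: chi-square 3.2, p = 0.07 (Fisher 0.12). The rule is not triggered.
- If population is tested as one three-level variable, 20:10 in the CAD group with the remainder shared equally (12.5:17.5 in each) gives p = 0.08. The rule is not triggered.

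**The case against.** A reader might infer that randomisation is not done within population. The documents do not support that: they are silent, and three groups of 30 followed by a statement that the study is randomised is compatible with randomising inside each group. The point stands only as something left unsecured.

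The size should not be overstated either. The 27% and 49% figures rest on assumed simple randomisation, and an overall 45:45 list brings them down to 11% and 26%. Chance imbalance under randomisation is not bias. A composition effect with SD 0.08 is small beside the standard error of a 45 v 45 comparison, √(2/45) = 0.21 SD. It is also a difference in level, which largely cancels in the time-by-treatment test, so harm there requires CAD patients to change differently. Within a population, even a perfect 15:15 detects only 1.06 SD with 80% power, and stratifying does not cure that.

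The covariate rule is a partial safeguard. If disease group counts as a baseline variable, a 20:10 CAD split triggers it, and BMI is a fixed covariate that bears on the obese group. But the plan does not say that disease group counts, 19:11 escapes the rule, and none of the fixed covariates records CAD.

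A reader might also conclude that the matching serves no planned test and should be dropped. That does not follow. The factors of the factorial ANOVA are not listed, the general t-test and rank-test sentences are not confined to the drug arms, and comparable ages and sexes help when the three populations are described side by side.

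**Conclusion.** The point holds as a gap in the allocation rule. Nothing written secures balance of drug within the three populations that the purpose names, and the one balancing device described acts on a different contrast. Whether the trial in fact stratified cannot be told from the documents.

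If it did not, and allocation was 1:1, a 20:10 or worse split somewhere is a realistic possibility rather than a remote one, but its direct cost in precision is modest. The stronger reason to act is prognostic: moderate imbalance in CAD patients can pass unadjusted into the drug comparison. The size of that effect depends on how differently CAD patients change, on which the documents give no figure. The change is worth making because it is nearly free, not because the expected harm is large.

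**What to change.** Replace the allocation sentence in the Design section with: *Within each of the three populations patients are randomised 1:1 to GLP-1R agonist or metformin, using concealed permuted-block lists of varying size.*

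In the Statistical analysis section, name population as a between-subject factor beside treatment in the repeated-measures ANOVA, where it should be crossed with time so that the time-by-treatment test is adjusted, and in the factorial ANOVA. The analysis then reflects the stratification and does not depend on a baseline significance test to bring population in.

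The cost is three randomisation lists instead of one, and two between-subject degrees of freedom for population as a main effect. No extra patients or visits are needed. The age and sex matching may stay.

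### The repeated-measures ANOVA drops any patient missing one of a marker's four values, with no missing-data rule; a REML mixed model with one named test would use the partial records

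*Combined protocol and SAP*

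**What the plan says.** The longitudinal model in the Statistical analysis section is a repeated-measures ANOVA: "ANOVA (general linear model, SPSS 22, SPSS Inc, Chicago, Ill) for repeated measurements will be applied". Visit (baseline, 3, 6 and 12 months) is the within-patient factor and treatment the between-patient factor. Two results are taken from it. The F and P "values of the interaction between time of measurement of the examined markers and type of treatment will be calculated", and then "The F and P values of the comparison between treatments will be calculated". Neither is named as the deciding test. Covariance is handled in the classical way: "The Greenhouse-Geisser correction will be used when the sphericity assumption" fails Mauchly's test.

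Other parts of the section bear on the point. Non-normal data "will be analyzed after transformation into ranks". Separately, "Comparisons between baseline or post-treatment values of measured markers between the 2 treatment groups will be performed using factorial ANOVA". Baseline variables that differ between arms or matter clinically "will be included in multivariate models as covariates".

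Under Design, "The investigators will study three groups matched for age and sex", with 30 patients each, randomised between two treatments for a year.

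No section gives a dropout rate, an analysis set, an imputation method or any rule for missing values. The document does not say in words that incomplete patients are left out; that follows from the procedure it names.

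**The concern.** A general-linear-model repeated-measures ANOVA with Mauchly's test and the Greenhouse-Geisser correction works on one row per patient. A patient without one of the four values of a marker leaves that marker's model altogether, and the values that were observed are discarded. Exclusion is marker by marker, so different markers can rest on different subsets of the randomised patients.

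The study's purpose is to examine changes under treatment, and the time-by-treatment test is the only explicit between-arm test of change. If values are missing completely at random, only precision is lost. If dropout depends on earlier observed values, and does so differently in the two arms, the completers are no longer comparable and the test can be biased. A correctly specified REML mixed model is approximately unbiased in that situation (missing at random), because it uses the partial records.

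The problem is confined to this model. The single-visit tests and the factorial ANOVA can use every patient seen at a visit, although they compare values at that visit and not change.

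**Working it through.** **Inputs from the document:** 3 × 30 = 90 patients, four visits, two arms, significance at 0.05. There is no stated power, SD, effect size or dropout, so there is no figure of the plan's to reproduce.

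**Assumptions:** 45 per arm (the allocation ratio is not given), SD 1, correlation 0.7 between any two visits, three cohorts of 30, baseline always observed. Simulations used 10,000 trials for complete data and for 3% misses, and 4,000 for the other results below. The Monte Carlo standard error is about 0.003 at a 5% rejection rate, 0.005 at 11%, 0.006 for power and 0.003 for bias. The ANOVA applied Greenhouse-Geisser only when Mauchly's p < 0.05. The mixed model kept all four visits as outcomes (REML, unstructured covariance, Hotelling-scaled Wald F).

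**1. Random intermittent misses at rate m per follow-up visit.** Complete records = 90(1 − m)³. For completers, SE of the month-12 change contrast = √[2(1 − 0.7) × 4/n] = √(2.4/n); for example √(2.4/65.6) = 0.191.

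| m | Complete records | SE, completers | SE, mixed model | ANOVA power | Mixed-model power |
|---|---|---|---|---|---|
| 3% | 82.1 | 0.171 | 0.165 | 85.6% | 87.5% |
| 5% | 77.2 | 0.176 | 0.166 | 83.0% | 86.9% |
| 10% | 65.6 | 0.191 | 0.169 | 76.0% | 85.6% |

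Power is for the time-by-treatment test with a constant 0.5 SD effect from month 3. There is no bias.

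**2. Random monotone dropout after month 3, 20% v 5%.** SE 0.174 v 0.171, no bias.

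**3. Same rates, but dropout in the 20% arm follows the month-3 change.** logit(p) = a + s·z, where z is the month-3 change standardised to SD 1 and a is set to give 20%. The other arm loses 5% at random. There is no true effect.

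| s | Completer bias, month 3 | Completer bias, month 12 | ANOVA rejects | Mixed model rejects |
|---|---|---|---|---|
| 0 | −0.006 | −0.002 | 5.0% | 4.8% |
| 0.5 | −0.078 | −0.039 | 6.1% | 4.4% |
| 1.0 | −0.137 | −0.068 | 8.2% | 4.7% |
| 1.5 | −0.178 | −0.089 | 11.5% | 5.2% |

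Mixed-model bias stays within 0.005 SD. The month-12 bias is half the month-3 bias, because the month-3 and month-12 changes have covariance 1 − 0.7 = 0.3 against a variance of 0.6. The month-12 value has covariance 0.7 − 0.7 = 0 with the month-3 change, so a comparison of month-12 values is unbiased here. Repeat runs with separate code gave 6.2%, 8.6% and 11.2% for the ANOVA, and a further run about 6% to 10%, so the last digits should not be leaned on.

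Variants at s = 1.5:
- Both arms driven, 20% each: bias −0.001, ANOVA rejection 5.2%.
- Both arms driven, 20% v 5%: bias −0.064, ANOVA 8.0%, mixed model 5.2%.
- One arm driven by the month-3 level: the month-12 value difference is biased by −0.156 SD, ANOVA 6.5%, mixed model 5.0%.

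**4. Missing not at random, s = 1.5, completers v mixed model.** Driven by the unseen 12-month change: month-12 bias −0.175 v −0.127, rejection 11.2% v 8.6%. Driven by the unseen change from month 3 to 12: −0.090 v −0.127, rejection 10.8% v 9.0%.

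**5. Different assumptions:** correlation 0.6, effect growing to 0.5 SD at month 12, Kenward-Roger F, 2,000 trials. Power, ANOVA v mixed model: complete data 0.63 v 0.63; monotone dropout of 20% 0.51 v 0.54 and of 30% 0.47 v 0.52; intermittent misses of 5% 0.55 v 0.60 and of 10% 0.47 v 0.58. With dropout tied to the last observed value in opposite directions by arm and no true effect, the month-12 estimate was 0.08 from completers and 0.005 from the mixed model. Null rejection was similar there (6.3% v 6.5%).

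**The case against.** The strongest reply is that the document shows no harm. Apart from the 90 patients, four visits, two arms and the 0.05 level, every input is assumed. Exclusion is inferred from the method's name, and silence on missing data does not rule out handling it beforehand. The bias needs particular conditions: none arises with random misses, random unequal dropout, or equal outcome-driven dropout in both arms. The 11.5% figure needs a steep slope in one arm, random loss in the other, and 20% v 5%. When values are missing not at random, the replacement fails as well and can be the more biased of the two. All of this stands, and it limits the weight of the point.

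A second reply is that the factorial ANOVA already protects the comparison. Under randomisation, the expected arm difference in month-12 values equals the expected difference in change, and that analysis can use every patient seen. This stands for change-driven dropout: the comparison is unbiased in the cases above, and within 0.03 SD under two decaying correlation structures. It does not stand when dropout follows the month-3 level in one arm, where the bias is 0.16 SD.

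A third reply is that power depends on the assumed shape of the effect. That also stands. With a gradual effect the complete-data power is only 63% for either method, and the gain under monotone dropout is about 0 to 6 points. Intermittent misses favour the mixed model under both sets of assumptions.

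**Conclusion.** The point holds as a worthwhile, inexpensive improvement; it does not demonstrate an error in any result. The named procedure analyses completers of each marker, there is no missing-data rule, and neither of the two tests from the model is named as deciding.

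The gain is negligible under random monotone dropout. It reaches about 10 to 11 power points at 10% intermittent misses. It is greatest where dropout follows observed values differently by arm: there the completers' change contrast was biased by up to 0.09 SD at month 12 and 0.18 SD at month 3, while the mixed model was essentially unbiased. These sizes rest on assumed dropout rates and mechanisms, equal allocation, and a correlation of 0.6 or 0.7. The mixed model's advantage rests on missing at random, which nothing in the document assures.

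**What to change.** Replace the ANOVA with a linear mixed model fitted by REML, with unstructured within-patient covariance, Kenward-Roger or Satterthwaite degrees of freedom where the software offers them, and patients in their randomised arm. Choose one of two forms in advance, with its 3-df test as the deciding test and the month-12 contrast reported alongside:

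- **(a)** All four visits as outcomes, with treatment, visit, treatment-by-visit and cohort. Include every patient with at least one value of the marker. The test is the 3-df time-by-treatment test.
- **(b)** Baseline and baseline-by-visit as covariates, with treatment, visit, treatment-by-visit and cohort. Include patients with a baseline and at least one later value. The test is the 3-df joint test of no treatment difference at 3, 6 and 12 months. Do not use the 2-df treatment-by-visit interaction as the test of effect: with complete data and a constant 0.5 SD effect it rejects in 5.1% of trials, against 94.8% for the joint test.

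With complete data, (b)'s power advantage over (a) (94.8% v 88.1%) comes from baseline adjustment and a different test, not from handling missing values.

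Carry the planned covariates (HbA1c, weight, BMI, waist circumference and imbalanced baseline variables) into the adjusted version. For skewed markers prefer a log or similar transformation: ranking the observed values visit by visit weakens the missing-at-random argument, and in simulation gave 79% to 80% power against 86% to 87% on the log scale. Keep the complete-case ANOVA as a sensitivity analysis. Add one for missing not at random: impute under missing at random, then shift by a stated range of SD units in each arm.

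The cost is SAP wording and slightly more analysis work, with no new data. Downsides: reliance on missing at random; about 1 point of power under (a) if nothing is missing and sphericity holds (88.1% v 89.1%); loss under (b) of baseline-only patients and those without a baseline; and a patient missing a covariate still leaves the adjusted version.

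### The purpose is set in three populations of 30, but the analysis names only treatment and time, and does not say whether the populations are pooled or analysed separately

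*Combined protocol and SAP*

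**What the plan says.** The Objectives section names the patients in whom changes are to be studied: T2DM without CAD, then "patients with T2DM and CAD and obese patients with abnormal oral glucose tolerance test (OGTT), changes in arterial stiffness" and the other vascular measures. The Design section repeats the structure: "The investigators will study three groups matched for age and sex", made up of "30 patients with type 2 diabetes mellitus (T2DM) without coronary artery disease (CAD), 30 patients with T2DM and CAD" and 30 obese patients with an abnormal OGTT. Each patient is randomised to a GLP-1R agonist or metformin.

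The Statistical analysis section names time (0, 3, 6 and 12 months) as the within-subject factor. The other term is "for the effects of treatment (liraglutide vs metformin), as a between-subject factors". Two results are asked for:
- the interaction: F and P "values of the interaction between time of measurement of the examined markers and type of treatment will be calculated";
- the main effect: "The F and P values of the comparison between treatments will be calculated".

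It then adds: "Comparisons between baseline or post-treatment values of measured markers between the 2 treatment groups will be performed using factorial ANOVA". The factors of that ANOVA are not listed. Covariates are baseline variables that differ at p<0.05 between the two study groups, or that matter clinically; the clinical list is HbA1c, weight, BMI and waist circumference.

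**The concern.** The question is put to three populations and the sample is built from them, yet no sentence of the analysis uses population. No treatment-by-population term and no treatment estimate within a population is stated, and the set of patients entering each ANOVA is left open.

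Two things are at stake. The first is the answer itself. If the populations are pooled, a benefit confined to two of them would be reported as a smaller benefit for all, and any later result by population would be unplanned. The second, less important, is precision. In a pooled analysis, differences between populations stay in the error term of the between-treatment F and of unadjusted post-treatment comparisons, apart from what the planned covariates absorb. None of the four listed covariates records CAD status, which is what separates the first two populations.

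**Working it through.** **Reading.** The gap shows from the text alone. Objectives and Design: three populations, 30 + 30 + 30 = 90. Statistical analysis: treatment, time, and their interaction. Population could enter under the covariate rule through an imbalance between arms at p<0.05. If allocation is not stratified, chance gives this in about 4.4% (45:45) to 4.8% (simple randomisation) of allocations; with stratification it is close to never. It could also enter by clinical judgement, but it is not on the clinical list. Either way it would be an adjustment, not an estimate for each population.

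**Size.** The documents give no SD, effect size or power, so there is no stated figure to reproduce. What follows is illustration.

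Assumptions, none in the documents: 1:1 allocation (45 per arm, 15 v 15 within a population), no dropout, two-sided 5%, total variance 1, correlation 0.6 between visits, effect 0.5 SD at 3, 6 and 12 months, and population explaining a share s = 10, 20 or 30% of variance. Powers come from the noncentral t.

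*Between-treatment F.* This compares four-visit means, so the effect is 0.5 × 3/4 = 0.375. The variance of a patient's mean is (1 + 3 × 0.6)/4 = 0.70, or 0.70 − s with population in the model.
- Without: SE = √(0.70 × 2/45) = 0.176; 0.375/0.176 = 2.13; power 56%.
- With: SE = 0.163 / 0.149 / 0.133; ratios 2.30 / 2.52 / 2.81; power 62 / 70 / 79%.

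*Unadjusted 12-month values.* The variance falls from 1 to w = 1 − s: power 65% without, about 70 / 75 / 80% with.

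*Baseline-adjusted 12-month values.* Without: variance 1 − 0.6² = 0.64, power 83%. With: within-population correlation r = (0.6 − s)/w = 0.556 / 0.500 / 0.429 and variance w(1 − r²) = 0.622 / 0.600 / 0.571, power 84 / 86 / 87%. The gain is 0 to 4 points (simulation: 84 / 84 / 86%). The plan does not list the baseline marker value as a covariate, so this comparison is itself an addition.

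*Time by treatment.* Its error is within patients and contains no population differences. Simulated power is 78% without and 77% with population.

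Simulation of 6,000 trials agrees: F 56% rising to 62 / 70 / 79%. These gains are upper bounds. If the planned covariates absorb half the population share, F goes from 58 / 61 / 65% to 61 / 69 / 78%.

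**What estimates by population can show** (15 v 15, baseline-adjusted).
- SE of one difference = √(w(1 − r²) × 2/15) = 0.288 / 0.283 / 0.276. The 95% half-width is t(27) = 2.052 times this: 0.59 / 0.58 / 0.57 SD. Unadjusted, t(28) × √(w × 2/15) = 0.71 / 0.67 / 0.63 SD. With 10 v 20 the adjusted widths grow by √(0.150/0.133) = 1.06, to 0.60–0.63 SD.
- True effects 0.5 / 0.5 / 0 SD: the pooled effect averages 1.0/3 = 0.33 SD. Interaction noncentrality = (2 × 0.167² + 0.333²)/SE² = 0.167/SE² = 2.0 to 2.2, giving about 22–24% power on 2 and 83 df (simulation 21–23%). The no-benefit population ranks lowest in about 81–82% of trials.
- True effect 0.5 SD in all three: the mean gap between highest and lowest estimate is (3/√π) × SE = 1.693 × 0.276 to 0.288 = 0.47–0.49 SD. The gap is at least 0.5 SD in about 41–46% of simulated trials.

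**If the ANOVA is run in each population.** A 0.5 SD effect tested 15 v 15 on unadjusted 12-month values has about 29 / 32 / 35% power.

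**The case against.** The strongest reply is that pooling is nowhere written. The plan does not say which patients enter the ANOVA, and a comparison of two treatment groups fits an analysis run inside each population equally well. The words factorial and factors, and the correction "Post hoc comparisons will be performed with Bonferroni correction. Statistical significance will be considered as" p<0.05, may point to a further factor. This stands. A reader might infer that the plan commits itself to one average over 90 patients; the text does not support that. What it supports is that the choice is open, and that neither reading gives adequately supported results by population.

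Second, the 81–82% ranking figure might be taken to mean that estimates by population would reliably expose a population without benefit. They would not. Some population always ranks lowest, and with identical effects a gap of 0.5 SD or more appears in over 40% of trials.

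Third, precision is a weak argument. The large gains apply only to the between-treatment F, which averages in the pre-treatment visit, and to unadjusted values; they also need a large population share. This stands too.

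Finally, a reader might infer that leaving population out biases the treatment comparison. Under randomisation it does not, on average.

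**Conclusion.** The point holds as an unstated element of the analysis. The purpose names three populations, the analysis names none, and the plan does not say whether they are pooled. It should be fixed, but it does not invalidate the randomised comparison. The main gain is a planned and honestly labelled estimate for each population. Precision is secondary: at most from about 56% to 62–79% for the between-treatment F, 0 to 4 points for a baseline-adjusted 12-month comparison, and nothing for time by treatment. The reading of the text needs no calculation. The sizes rest wholly on the assumed allocation, correlation, population share and effect.

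**What to change.** 1. State that the primary treatment comparison uses all 90 patients, with population (three levels) as a between-subject factor in every ANOVA treatment comparison, beside the planned covariates.
2. In a second model, add the treatment-by-population term.
3. For arterial stiffness, PBR and CFR, report the 12-month treatment difference with 95% CI in each population, as estimation only and with no significance claims within a population. For non-normal markers give a rank-based estimate and interval, such as Hodges–Lehmann. State that differences between populations are descriptive.

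Adjusting for the baseline marker value would narrow the intervals, but it is a separate, additional change to the covariate list.

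Cost: a few sentences, no new data, 2 degrees of freedom for population and 2 more for the interaction. The price in interpretation is wide intervals, wider still if allocation is unequal, and an interaction test that cannot settle whether effects differ.

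### Does the analysis compare a different pair of treatments (liraglutide against metformin) from the pair that was randomised (GLP-1R agonist against metformin)?

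*Combined protocol and SAP*

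**What the plan says.** The Design section describes the allocation by drug class: "It will be a randomized study with metformin or GLP-1R agonist treatment for 1 year", and then "All subjects will receive for 1 year: (a) GLP-1R agonist or (b) metformin". The purpose statement in Objectives uses the same class-level wording, "after treatment with metformin or agonist GLP-1R". The title also speaks of the class.

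Individual agents are named in two places only. One is the background text in Objectives, which says of the class: "This category includes exenatide and liraglutide". The other is the Statistical analysis section, where the between-subject factor of the repeated-measures ANOVA is specified "for the effects of treatment (liraglutide vs metformin), as a between-subject factors". The next model in that section compares baseline or post-treatment values "between the 2 treatment groups will be performed using factorial ANOVA", without naming an agent.

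No sentence says which agonist is given, that liraglutide is the only one, or how a patient on another agonist would be analysed.

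**The concern.** A treatment factor should carry the same definition in the analysis as in the randomisation. Here the arm is a class with two named members, and the factor is one of those members. On a literal reading, a patient randomised to the agonist arm and given exenatide has no level in the ANOVA. That patient would be left out or counted under the wrong drug.

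Leaving patients out according to the agonist they received would be an exclusion after randomisation, in one arm only. It could bias the comparison and would reduce its precision. In the opposite case, with every agonist patient on liraglutide, the title and purpose could invite a conclusion about the class from a trial of one agent.

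**Working it through.** **The passages side by side**

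| Place | Agonist arm called | Comparator |
|---|---|---|
| Objectives, purpose | agonist of the class | metformin |
| Design | agonist of the class | metformin |
| Statistical analysis, repeated-measures ANOVA | liraglutide | metformin |
| Statistical analysis, factorial ANOVA | one of two treatment groups | the other group |

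Every row has two arms. The Design offers options (a) and (b) and no third. The one sentence that mentions exenatide describes the class and does not list study drugs. No passage excludes anyone by agent; the word liraglutide stands in a bracket that labels the factor.

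**What each reading does to the analysis**

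1. Liraglutide is the only agonist. The factor and the randomised arm contain the same patients, and nothing changes.
2. More than one agonist is used and the factor is coded by randomised arm. The same patients are compared again. The label is inexact, but the estimate, F and P values are those of the randomised comparison.
3. More than one agonist is used and patients on the others are dropped. Only here does the analysed contrast depart from the randomised one. The documents contain neither of the two conditions this reading needs.

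**Size under the third reading**

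The plan gives no power calculation, so there is no figure of its own to reproduce. The Design gives three groups of 30, so the total is 3 × 30 = 90. The following are assumptions, not statements in the documents: a 45:45 split, a fraction *f* of the agonist arm on another agent and dropped, two-sided 0.05 and 80% power.

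The standard error relative to the full comparison is

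sqrt[(1/(45(1−*f*)) + 1/45) / (2/45)]

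- *f* = 0: ratio 1.00
- *f* = 0.25: sqrt(1.167) = 1.08, an 8% rise
- *f* = 0.50: sqrt(1.5) = 1.22, a 22% rise

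The detectable difference in SD units is (1.96 + 0.84) × sqrt(1/45 + 1/(45(1−*f*))). Power is for an assumed true difference of 0.6 SD.

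| *f* | Agonist patients kept | Detectable difference | Power at 0.6 SD |
|---|---|---|---|
| 0 | 45 | 0.59 | 81% |
| 0.25 | 33.75 | 0.64 | 75% |
| 0.50 | 22.5 | 0.72 | 64% |

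The arithmetic is sound, but *f* is invented. On the first two readings nobody is dropped, and the first row applies.

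**The case for a change.** The best argument for a change is that both outcomes leave something to correct. If several agonists are allowed, the factor has no level for the others, and the reference to two treatment groups does not settle the matter, because it fits a mislabelled class arm as well as a single-agent arm. If only liraglutide is used, the Design does not name the drug under test. In both cases a reader cannot learn from the documents exactly what the intervention is, and a few words would cure that at no cost.

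The observation about wording stands: the two terms are different and unreconciled, and naming the agent would make the document clearer. The step from there to a faulty analysis does not stand. It needs a second study drug that no passage assigns and an exclusion that no passage prescribes. The worry about a class-wide claim is also weak, since the plan uses the class name for its title, purpose and arms but states no conclusion about the class. How far the results extend beyond the agent used is a matter for the report.

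**Conclusion.** The concern does not hold as a fault in the analysis. The mismatch between the class name in the Design and the agent name in the ANOVA is real, but it is an omitted detail. The most natural reading is a two-arm trial with liraglutide as the agonist, under which the randomised and analysed contrasts coincide and the effect on precision is zero. If another agonist were in use, an analyst following the two-group structure would still compare the randomised arms, and only the label would be imprecise.

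The increases of 8% and 22% in standard error apply only if a quarter or a half of an assumed 45 agonist patients took another drug and were then removed. The documents give no ground for either step. The judgement rests on patients being compared by the arm to which they were randomised, which is how the two treatment groups are ordinarily understood. Stating the agent would be good housekeeping, but it would not alter any documented analysis or result.
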